10.3. General Statistical Considerations

The statistical analyses will be performed using R, version 4.4.0 or higher. Any statistical tests of hypotheses will employ a level of significance of $\alpha=0.05$.

11. SAMPLE SIZE JUSTIFICATION

Assuming an effect size of 0.5, α 0.05, and power 90%, we estimate the study will require 46 subjects. To account for 15% dropout, the sample size will be increased to 54.

12. CONFIDENTIALITY/PUBLICATION OF THE STUDY

The existence of this Study is confidential and should not be discussed with persons outside of the Study. Results will be submitted for publication and presentation at national and/or international meetings. A manuscript will be submitted to peer-review journals for publication but there is no guarantee of acceptance.

All study data will be collected on appropriate Case Report Forms (CRFs). No protected health information will be included on the forms. CRFs will be retained in the patient's file for a minimum period of 3 years. Collected information will only be used for purposes of this study and no information will be sold to third parties. The following people will have access to your study records:

- Study Doctor and staff involved with the study
- Study Monitor or Auditor
- Sponsor Company or Research Institution
- Review boards or accrediting agencies
- Other State or Federal Regulatory Agencies

The de-identified data may be shared with other researchers for future analysis.

13. QUALITY COMPLAINTS AND ADVERSE EVENTS

All subjects will be monitored for adverse events over the course of the study. A place to record any adverse event is included on each case report form.

13.1. General Information

An Adverse Event (AE) is any untoward medical occurrence in a subject who is administered a study treatment regardless of whether or not the event has a causal relationship with the treatment. An AE, therefore, can be any unfavorable or unintended sign (including an abnormal laboratory finding), symptom, or disease temporally associated with the study treatment, whether or not related to the treatment. In clinical studies, an AE can include an untoward medical occurrence occurring at any time, including run-in or washout periods, even if no study treatment has been administered.

13.2. Monitoring for Adverse Events

At each visit, after the subject has had the opportunity to spontaneously mention any problems, the Investigator should inquire about AEs by asking if the patient has any problems.

13.3. Procedures for Recording and Reporting AEs and SAEs

Subsequent to signing an informed consent form, all untoward medical occurrences that occur during the course of the study must be documented on an Adverse Event Form (AEF). A separate AEF must be filled out for each event. When possible, signs and symptoms indicating a common underlying pathology should be documented as one comprehensive event. For each recorded event, the AE documentation must include the onset date, outcome, resolution date (if event is resolved), intensity (i.e., severity), any action with study treatment taken as a result of the event, and an assessment of the adverse event's relationship to the study treatment.

Nonserious Adverse Events

A nonserious AE is defined as any untoward change in a subject's medical health that does not meet serious criteria noted below (e.g., is not life-threatening, does not require hospitalization, does not prolong a current hospitalization, is not disabling, etc.). All adverse events must be reported regardless of whether or not they are related to the study treatment.

For nonserious adverse events, an AEF containing all available information will be collected on a routine basis and submitted to the Medical Monitor at the close of the study.

Serious Adverse Events

A serious adverse event (SAE) is defined as any adverse experience that meets any of the following criteria:

- Results in death.
- Is life-threatening.

- NOTE: Life-threatening means that the subject was at immediate risk of death from the reaction as it occurred; i.e., it does not include a reaction which hypothetically might have caused death had it occurred in a more severe form.
- Requires inpatient hospitalization or prolongation of existing hospitalization.
NOTE: In general, hospitalization signifies that the individual remained at the hospital or emergency ward for observation and/or treatment (usually involving an overnight stay) that would not have been appropriate in the physician's office or an out-patient setting. Complications that occur during hospitalization are AEs. If a complication prolongs hospitalization or fulfills any other serious criteria, the event is serious. When in doubt as to whether "hospitalization" occurred, the event should be considered serious.
 - Results in persistent or significant disability/incapacity. Disability is defined as a substantial disruption of a person's ability to conduct normal life functions.
NOTE: The term disability means a substantial disruption of a person's ability to conduct normal life functions. This definition is not intended to include experiences of relatively minor medical significance such as uncomplicated headache, nausea, vomiting, diarrhea, influenza, or accidental trauma (e.g., sprained ankle) which may interfere or prevent everyday life functions but do not constitute a substantial disruption.
 - Is an important medical event. An important medical event is an event that may not result in death, be life-threatening, or require hospitalization but may be considered an SAE when, based upon appropriate medical judgment, it may jeopardize the subject and may require medical or surgical intervention to prevent one of the outcomes listed in the definitions for SAEs. Examples of such medical events include allergic bronchospasm requiring intensive treatment in an emergency room or at home, blood dyscrasias or convulsions that do not result in subject hospitalization, or the development of drug dependency or drug abuse.
All available information on a serious adverse event(s) and any other associated AE, if applicable, must be forwarded to the study coordinator for forwarding to the Medical Monitor immediately (i.e., within one working day of the Investigator's or site's knowledge of the event) as follows:
 - In studies utilizing EDC (electronic data capture), all available information for the SAE and any associated AE(s) must be entered immediately into the EDC system.
 - Additional information for any applicable event is to be reported as soon as it becomes available.

In addition to the reporting of serious adverse events to the study Medical Monitor, the SAE must be reported to the IRB / IEC according to their requirements.

The investigator must document all adverse device events (serious and nonserious but related) and all serious adverse events (related and unrelated) on the Adverse Device Effect and Serious Adverse Event Form. Any device quality complaints will also be documented.

- **Both the Quality Complaint Form and the Adverse Device Effect and Serious Adverse Event Form must be e-mailed immediately to the study coordinator.**
- **Additional relevant information is to be reported as soon as it becomes available.**

Study coordinator contact information is provided below.

**Table 13.3.-1:
Contact Information for the Study**

Study Staff (Coordinator)	Business Phone	e-mail	24-hour Office Phone

12.3.1 Intensity and Causality Assessments

For every adverse event and quality complaint, the investigator must assess the causality as Related or Not Related to the medical device under investigation. An assessment of causality will also be performed by the Medical Monitor utilizing the same definitions, as shown below:

Causality

- | | |
|-------------|--|
| Related | An adverse event or quality complaint classified as related may be either definitely related or possibly related where a direct cause and effect relationship with the medical device has not been demonstrated, but there is a reasonable possibility that the adverse event or quality complaint was caused by the medical device. |
| Not Related | An adverse event or quality complaint classified as not related may either be definitely unrelated or simply unlikely to be related (i.e., there are other more likely causes for the adverse event or quality complaint). |

Where appropriate, the investigator must assess the intensity (severity) of the adverse event as mild, moderate, or severe based on medical judgment with consideration of any subjective symptom(s), as defined below:

Intensity (Severity)

Mild	An adverse event is mild if the subject is aware of but can easily tolerate the sign or symptom.
Moderate	An adverse event is moderate if the sign or symptom results in discomfort significant enough to cause interference with the subject's usual activities.
Severe	An adverse event is severe if the sign or symptom is incapacitating and results in the subject's inability to work or engage in their usual activities.

The investigator must document any action taken (i.e., medication, intervention, or treatment plan) and outcome of the adverse event or quality complaint when applicable.

13.4. Follow-Up of Adverse Events and Quality Complaints

The investigator is responsible for adequate and safe medical care of subjects during the study and for ensuring that appropriate medical care and relevant follow-up procedures are maintained after the study. Any additional data from these follow-up procedures must be documented and available to the study coordinator who, with the Medical Monitor, will determine when the data need to be documented on the CRFs.

13.5. Safety Analyses

The type, severity, duration and frequency of reported ocular adverse events will be tabulated. Adverse events will also be summarized for events that were considered treatment-related.

14. GCP, ICH and ETHICAL CONSIDERATIONS

This study will be conducted in compliance with Good Clinical Practices (GCPs), including International Harmonization (ICH) Guidelines, and in general, consistent with the 1996 version of the Declaration of Helsinki. In addition, all applicable local, state and federal requirements will be adhered to.

This study is to be conducted in accordance with Institutional Review Board regulations. The investigator will obtain appropriate IRB/ethics committee approval prior to initiating the study.

The study will be registered with clinicaltrials.gov.

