10. ANALYSIS PLAN

10.1. Analysis Data Sets

All subjects who are enrolled in the study will be evaluated for safety. Efficacy analyses will be performed based on data from those eyes where the visit was completed.

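### Section 13.5 leaves non-ocular adverse events judged not related out of every planned summary, and the plan does not secure attribution of events to one of the three devices

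*Combined protocol and SAP*

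**What the plan says.** Section 10.1 sets a broad safety population: "All subjects who are enrolled in the study will be evaluated for safety". Section 13.3 sets an equally broad collection rule: "All adverse events must be reported regardless of whether or not they are related to the study treatment".

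Section 13.5 then names two summaries. The main one reads "The type, severity, duration and frequency of reported ocular adverse events will be tabulated". The other reads "Adverse events will also be summarized for events that were considered treatment-related". Neither mentions device or test order.

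On what is recorded for each event, section 13.3 says that "the AE documentation must include the onset date, outcome, resolution date (if event is resolved), intensity (i.e., severity"), followed by any action taken with the study treatment and "an assessment of the adverse event's relationship to the study treatment". The subsection numbered 12.3.1, which sits within section 13, says that "the investigator must assess the causality as Related or Not Related to the medical device under investigation". Both refer to one treatment or one device. Section 3 lists three test articles, section 8.3 has every subject tested on all three in random order, and sections 9.2 and 9.3.1 put them in a single visit with five-minute rests between devices.

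**The concern.** The plan collects more safety data than it undertakes to summarise. The restriction to ocular events is stated, so an analyst who follows section 13.5 literally will leave out non-ocular events judged not related. For a non-ocular event, such as a headache or dizziness around the time of testing, the only way into a table is a judgement of relatedness, made in an unmasked study.

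The second issue is attribution. The study exists to compare devices, but nothing in the plan requires an adverse event to be tied to one of them. The table can be redone at any time. Which device was in use at onset may not be recoverable if it was not written down during the visit.

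**Working it through.** The plan gives no expected adverse event rate and no figure for this point, so the check is mainly a reading of the sections side by side.

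**1. Which events reach a planned summary (section 13.5)**

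| Event | Ocular tabulation | Treatment-related summary |
|---|---|---|
| Ocular, related | yes | yes |
| Ocular, not related | yes | no |
| Non-ocular, related | no | yes |
| Non-ocular, not related | no | no |

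Three of the four classes are covered. The fourth is in neither summary, although sections 10.1 and 13.3 bring it within safety evaluation and collection.

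**2. Whether the required items identify a device**

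- Timing: section 13.3 asks for the onset date. All three devices are used at one visit, so the date is the same for each and cannot separate them. Onset time is not among the listed items.
- Relationship: section 13.3 refers to the study treatment and 12.3.1 to the device under investigation, both singular. A related judgement satisfies the text without saying which perimeter is meant.
- Ascertainment: section 13.2 asks about events at each visit, not after each device, and Table 15.1 has one row for adverse event monitoring.
- Randomised order (section 8.3) gives the sequence of devices, but without an onset time it does not place an event within that sequence.

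No section requires the device to be named.

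**3. What pooling can and cannot show**

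Inputs: 54 subjects and 15% dropout (section 11); three devices (section 3). Section 11 inflates 46 as 46/(1 − 0.15) = 54.1, stated as 54.

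- Device exposures if everyone completes: 54 × 3 = 162.
- Hypothetical pooled table with six affected subjects: all on one device gives 6/54 = 11.1% for that device; two on each gives 2/54 = 3.7% per device. The pooled table looks the same in both cases. The six is chosen for illustration only.
- With no event on a device, the one-sided 95% upper bound on its rate is 1 − 0.05^(1/n). For n = 54 this is 5.4%; for n = 46, the number before the dropout allowance, it is 6.3%.
- If the pooled count is zero, the count on each device is also zero, so the same bound follows from the pooled table for the event types it covers. More generally, if x subjects are affected in the pooled table and all 54 used every device, no device can exceed x/54. Pooling loses information only when there are events to distribute.

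**The case against.** Four points can be made for the plan.

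- A reader might infer that the omitted events are lost. The documents do not support that. Every untoward occurrence goes on an Adverse Event Form, non-serious forms go to the Medical Monitor at study close, and serious events, related or not, go to the Medical Monitor and the ethics board (section 13.3). The events are absent from the summaries, not from the record.
- A reader might infer that one unmasked investigator alone decides which non-ocular events appear. Subsection 12.3.1 also has the Medical Monitor assess causality, and it defines related to include any event with a reasonable possibility of device causation. Many symptoms during testing would meet that and enter the second summary, so the uncovered class is probably small. It still exists, and section 13.5 does not say whose assessment counts if the two differ.
- A reader might infer that no event can be attributed to a device. That goes too far. Section 13.3 refers to an adverse device effect form and a quality complaint form whose fields are not shown, and an investigator could name the device. What stands is that the plan does not require it.
- On by-device presentation, section 13.5 is silent; it does not prescribe pooling. An analyst could split the table without contradicting the text, but only if the device had been recorded.

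It is also fair that safety is not among the objectives or outcomes in sections 3, 6 and 8.1, and that section 19.1 describes risks like those of any visual field testing. This limits the importance of the point without removing it.

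**Conclusion.** The point holds in a limited form. Section 13.5 omits one class of collected events, non-ocular and judged not related, from every planned summary. No by-device presentation is planned, and the required record items do not secure attribution among three devices used at the same visit.

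The size is modest. No primary or secondary conclusion changes and no sample size figure is affected. That few events will occur is an inference from section 19.1, since the documents give no rate. The percentages above illustrate what pooling hides; they do not predict the result, and they assume that all 54 subjects use every device. The conclusion on attribution rests on the items listed in section 13.3 and subsection 12.3.1, and would weaken if the device forms already carry a mandatory device field. The change is worth making before enrolment because the device at onset may not be recoverable afterwards.

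**What to change.** Change section 13.5 along these lines: *All adverse events, ocular and non-ocular, related and not related, will be tabulated overall and by device. The denominator for each device is the number of subjects exposed to it. Events with onset before the first device, and events that cannot be attributed to one device, will be shown as separate categories.* The last category matters because the rests are short: assigning every rest-period or delayed symptom to the preceding device could misattribute cumulative fatigue.

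Require the adverse event record to give onset time and the device in use or suspected, unless the existing forms already do. Test position then follows from the randomised order. Reword the singular references in subsection 12.3.1 and section 13.3 so that causality is stated with respect to the three test articles.

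Cost: one or two extra items on the adverse event form, one more table dimension, and some events left unattributed. Sample size, endpoints and study procedures are unchanged.

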14.1 Confidentiality

The data collected will be data typical for the procedure(s) when performed on eyes outside the study. Any data collected will become part of the patient's clinical record. The data will be subject to the same privacy and confidentiality as other data in the clinical record.

Only the principal investigator, research consultant and clinic staff will have access to the data collected. All data shared outside the practice will be de-identified; patients' protected health information will not be available and will not be reported in any analyses or publications. No data will be sold to third parties. De-identified data may be used for future research.

15. STANDARD EVALUATION PROCEDURES

Table 15.1. Proposed Visits and Study Assessments

Activity	Visit 1
Informed Consent	X
Demographics	X
General Information: Medical History	X
Visual Field Testing with: TEMPO Virtual Eye ELITE HFA	X
Total set up time	X
Total acquisition time	X
Mean deviation (MD)	X
Pattern standard deviation (PSD)	X
Foveal threshold (FT)	X
Visual field index (VFI)	X
False positives/negatives	X
Optical coherence tomography (OCT)	X
Patient Questionnaire	X
Monitor for Adverse Events and Device Deficiencies	X
Complete Exit Form ¹	X

¹ Complete Exit Form upon termination of subject participation, or at the final visit, whichever occurs first.

16. DATA CONFIDENTIALITY

No protected health information (PHI), including the patient's name and date of birth, will be collected; to ensure this, no PHI information is permitted to be entered on any of the Case Report Forms (CRFs). Subjects will only be identified by subject IDs and identities will be removed at the initial visit so that there is no further need to protect or destroy the information. Collected information will only be used for purposes of this study and no information will be sold to third parties. The non-PHI information collected may be used for future research, though there is currently no plan to do so.

17. FINANCIAL AND INSURANCE INFORMATION/STUDY RELATED INJURIES

Every effort to prevent study-related injury will be taken by the Study Doctor and staff. In the event a patient is injured as a direct result of the study while following the Study Doctor's instructions and the study requirements, the patient will be instructed to contact his or her doctor immediately. The Study Doctor is to treat the injured subject as needed for those injuries caused directly by this research study. In the event of injury or illness

caused by or occurring during a subject's participation in this research study, all charges for medical care provided to the subject will be billed to his or her insurance company. The Study Doctor or Sponsor does not offer to cover the medical care costs for injuries or illnesses that are not caused directly by the research study. The Sponsor does not offer to provide any other compensation, unless specifically agreed to elsewhere in this document. This information will be provided to each study subject before the start of the study in the consent form.

18. STUDY ENDPOINT CRITERIA

18.1. Patient Completion of Study

If a study patient has completed the final visit of the study, he/she is considered to have completed the study.

18.2. Patient Discontinuation

Each study patient may voluntarily discontinue the study at any time they choose. Study patients who cannot complete the study for administrative reasons (e.g., non-compliance, failure to meet visit schedule, etc.) will be discontinued from the study. Study patients discontinued during the enrollment phase of the study will be replaced.

18.3. Patient Termination

A study patient will be terminated if the study patient develops any severe adverse event that may be related to the study. A study patient will receive appropriate treatment at the discretion of the investigator. Notification of termination will be clearly documented. These study patients are considered to have completed the study and will not be replaced.

18.4. Study Termination

The investigator with appropriate notification may terminate the study. If, after clinical observations, the investigator feels that it may be unwise to continue the study, he may stop the study.

18.5. Study Completion

The study will be complete when all enrolled patients have completed the final visit or have been terminated from the study.

19. SUMMARY OF RISKS AND BENEFITS

19.1. Summary of risks

The risks with this study are similar to those for any patient receiving visual field testing.^{1,2} There is no increased risk associated with the proposed study.

